### **Mid-term evaluation**

After 6 months of treatment, the patients of both study groups will be summoned to the Metabolism Research Laboratory of the University of Guanajuato León campus, with fasting from 8-12h for the completion of the OGTT, and the intermediate evaluation on the status of the glucose metabolism During this test blood samples will be taken at 0, 30, 60, 90 and 120 minutes to determine glucose and insulin, and obtain different rates of insulin resistance and insulin secretion. In addition, the evaluation of cardiovascular function and renal function will also be performed, using the methods previously mentioned. The hyperglycemic clamp will also be performed in the patients of both study groups.

### **Completion of the study (final measurements)**

At 12 months of treatment, patients will be cited again on an 8-12h fast, on two different occasions:

- 1) First appointment: OGTT will be performed for the measurement of glucose and insulin, determination of markers of inflammation and endothelial dysfunction will be made. Measurement of body composition will be done using impedance and DEXA.
- 2) Second appointment: The evaluation of cardiovascular function by echocardiography, and renal function by creatinine and albumin clearance in 24-hour urine will be performed.

### **Laboratory procedures and techniques**

For glucose measurement, an Analox GM9 brand glucoanalyzer will be used, which uses the glucose oxidase method. The measurement of TNF alpha, IL-6 and hsCRP will be done by ELISA or chemiluminescence in the Metabolism Research Laboratory of the University of Guanajuato; Insulin measurement will be done by chemiluminescence in the HRAEB laboratory. Lipid measurement, blood count, blood chemistry, liver function tests, will be done using standard techniques. For the determination of body composition, a DEXA equipment for bone densitometry and body composition with a worldwide standard methodology will be used.

Several methods will be used to calculate insulin resistance:

- 1) HOMA-IR = (Fasting plasma insulin in mU / l / Fasting plasma glucose in mmol / l) / 22.5; This only requires fasting glucose and insulin.
- 2) Matsuda index =  $10,000 / \sqrt{[(\text{fasting glucose in mg / dl} \times \text{fasting insulin in mU / l}) \times (\text{average glucose during OGTT} \times \text{average insulin during OGTT})]}$  [29]
- 3) QUICKI index =  $1 / (\text{fasting insulin log} + \text{fasting glucose log})$

The following methods will be used to calculate the beta cell function:

- 1) HOMA-B =  $(20 \times \text{fasting plasma insulin in mU / l}) / (\text{fasting glucose in mmol / l} - 3.5)$ , which requires fasting glucose and insulin
- 2) Calculation of insulin availability index during OGTT

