A chronological sequence has been proposed in the appearance of the different types of prediabetes [25, 45], which would be: i) isolated insulin resistance without fasting hyperglycemia or postprandial hyperglycemia, ii) isolated GAA, iii) isolated ITG, and iv) GAA + ITG, for the appearance of these 4 states the presence of insulin resistance (in liver, muscle and adipose tissue) and the dysfunction of the pancreatic beta cell are key; It is clear, by definition, that the diagnosis of the last three is made with the measurement of fasting glucose and the performance of the oral glucose tolerance curve (OGTT) with an oral load of 75 g of glucose, on the other hand, for the diagnosis of the first (isolated insulin resistance), there are several methods. One of the most used methods in epidemiological studies is the insulin resistance homeostasis model (HOMA-IR) which is obtained by fasting glucose and insulin by means of the following formula:  $HOMA-IR = \frac{\text{Plasma insulin fasting in mU} \times \text{Fasting plasma}}{1}$

glucose in mmol / l) /22.5; As already mentioned, fasting glucose is determined by the rate of hepatic glucose production, and fasting insulin is the main regulator of hepatic glucose production, so the product of both represents insulin resistance mainly at the liver level Said insulin resistance correlates 70-80% with insulin resistance at the peripheral level; In patients ranging from normoglycemia, prediabetes and even DM2, HOMA-IR has a correlation ranging from 0.6 to 0.88 with other more sensitive methods, such as the hyperinsulinemic-euglycemic clamp, considered as the gold standard for identifying resistance to insulin [56-62]. However, the cut-off point for HOMA-IR from which insulin resistance is detected has been variable in different studies, some have reported cut-off points of 2.7 [63], others of 2.6 with a specificity of up to 87% to identify insulin resistance [64,65], and it is generally accepted that a HOMA-IR greater than 3.0 is associated with insulin resistance.

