#### 5) Insulin Sensitivity (Matsuda Index)

- a. Type of variable and level of measurement: Dependent, Quantitative of reason
- b. Indicator: natural numbers
- c. Conceptual definition: The ability of insulin to promote glucose uptake by muscle tissue, to suppress glucose production by the liver and to prevent lipolysis in adipose tissue.
- d. Operational definition: It will be evaluated using the Matsuda index with glucose and insulin values during the OGTT using the following formula:

$$\text{Insulin sensitivity} = \frac{10000}{\sqrt{(G_0 \times I_0) \times (G_{0-120} \times I_{0-120})}}$$

Where  $G_0$  = basal glucose

$I_0$  = basal insulin

$G_{0-120}$  = average glucose during OGTT

$I_{0-120}$  = average insulin during OGTT

This measurement will be carried out at the beginning and at the end of the intervention in each of the study groups.

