- 1) Fasting baseline blood samples for measurement of: blood count, liver transaminases, lipid profile, inflammation markers (TNF alpha, IL-6, hsPCR, etc.) and insulin for the determination of HOMA-IR and HOMA- B.
- 2) Weight determination using a digital scale
- 3) Determination of body composition (% total fat, visceral fat,% total body water, bone mineral density, etc.) by DEXA analysis.

In this phase the screening of patients ends, and if at this time the patient agrees to continue in the intervention phase, the following will be done:

1) **Evaluation of cardiovascular function:** This will be done by standard echocardiography that will be performed in the Echocardiography area of the High Specialty Regional Hospital by a specialist in the area.

2) **Evaluation of renal function:** It will be carried out through 24-hour urine collection, in which creatinine clearance and 24-hour albuminuria will be measured.

3) **Randomization:** The patients will be randomized to one of the two interventions. It will be done by using a table of random numbers generated by a computer program. Patients will be randomized to receive, for 12 months, one of the following 2 interventions: 1) Quadruple therapy consisting of: 1 tablet every 24 h of linagliptin 2.5mg / metformin 850mg + 1 tablet every 24 h of empagliflozin 12.5mg / metformin 850mg + lifestyle modifications (personalized diet plan and individualized physical activity

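### The methods section computes HOMA-IR as insulin divided by glucose, although the protocol's own background defines it as their product

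*Combined protocol and SAP*

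**What the plan says.** Laboratory procedures and techniques introduces its list with "Several methods will be used to calculate insulin resistance". The list has three entries: HOMA-IR, the Matsuda index and QUICKI. The HOMA-IR entry reads "HOMA-IR = (Fasting plasma insulin in mU / l / Fasting plasma glucose in mmol / l) / 22.5", which is a ratio of insulin to glucose.

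The background section on prediabetes gives a different formula, fasting insulin multiplied by fasting glucose over 22.5. It explains that fasting glucose reflects hepatic glucose output and fasting insulin regulates it, "so the product of both represents insulin resistance mainly at the liver level". It then cites cut-offs of 2.7 and 2.6 from individual studies, and adds that "it is generally accepted that a HOMA-IR greater than 3.0 is associated with insulin resistance".

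HOMA-IR is a planned trial measurement. Under Patient Recruitment, the baseline fasting sample includes "insulin for the determination of HOMA-IR". The Mid-term evaluation repeats the OGTT with glucose and insulin to "obtain different rates of insulin resistance and insulin secretion". The defined dependent variable for insulin sensitivity is another index: "It will be evaluated using the Matsuda index with glucose and insulin values during the OGTT".

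**The concern.** Insulin resistance is named in the research question, the goal, specific goals 2, 3 and 5, and the hypothesis, and HOMA-IR is one of the three ways the protocol says it will be calculated. Dividing by glucose does more than rescale the index. A constant factor would leave percentage changes, t tests and Mann-Whitney tests intact. Here the exponent of glucose changes from +1 to −1, so patients can be ranked differently and changes over time can reverse.

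Both arms receive treatment meant to lower fasting glucose. When glucose falls and insulin falls by a smaller percentage, the written index rises and reports more resistance where the product form reports less. When insulin falls by a larger percentage, the improvement is understated. The analysis of changes between groups planned under Statistic Analysis would carry the error forward if HOMA-IR is among the variables analysed.

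**Working it through.** The documents report no HOMA-IR value, so there is no figure of the plan's to reproduce. The check evaluates both formulas over the trial's entry range.

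**Inputs**
- Fasting glucose at entry: 100–125 mg/dL (Inclusion Criteria). At 18.016 mg/dL per mmol/l this is 5.551–6.938 mmol/l.
- Cut-offs: 2.6, 2.7 and 3.0 (background on prediabetes).
- Fasting insulin: not given. Assumed range 5–30 mU/l, with 15 mU/l for single examples.

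**Formulas**, with I for insulin in mU/l and G for glucose in mmol/l
- Written (methods): (I / G) / 22.5, so log index = log I − log G − log 22.5
- Product (background): (I × G) / 22.5, so log index = log I + log G − log 22.5
- Product divided by written = G², which is 30.8 at 100 mg/dL and 48.1 at 125 mg/dL

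**Scale**
- Written, lowest: 5 / 6.938 / 22.5 = 0.032. Highest: 30 / 5.551 / 22.5 = 0.240.
- Product, lowest: 5 × 5.551 / 22.5 = 1.23. Highest: 30 × 6.938 / 22.5 = 9.25.
- Insulin needed to reach a cut-off c as written is c × 22.5 × G: from 2.6 × 22.5 × 5.551 = 325 to 3.0 × 22.5 × 6.938 = 468 mU/l.
- Insulin needed with the product is c × 22.5 / G: from 2.6 × 22.5 / 6.938 = 8.4 to 3.0 × 22.5 / 5.551 = 12.2 mU/l.

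The cited cut-offs fit only the product form.

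**Direction.** Glucose falls from 110 to 95 mg/dL (6.106 to 5.273 mmol/l, −13.6%) and insulin starts at 15 mU/l. At the start the written form is 0.1092 and the product form 4.070.

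| Insulin afterwards (mU/l) | Written | Change | Product | Change |
|---|---|---|---|---|
| 15 (unchanged) | 0.1264 | +15.8% | 3.515 | −13.6% |
| 12.95 (−13.6%) | 0.1092 | 0% | 3.036 | −25.4% |
| 12 (−20%) | 0.1011 | −7.4% | 2.812 | −30.9% |
| 10.5 (−30%) | 0.0885 | −18.9% | 2.461 | −39.5% |

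The break-even is 15 × 5.273 / 6.106 = 12.95 mU/l, where insulin and glucose fall by the same percentage. With a larger glucose fall, from 125 to 95 mg/dL (−24%), even a 20% fall in insulin (15 to 12) leaves the written form 5% higher (0.096 to 0.101), while the product form falls 39% (4.63 to 2.81).

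**Agreement with the other listed indices.** Matsuda contains fasting glucose multiplied by fasting insulin. QUICKI is the reciprocal of the sum of their logs, so it is a function of the same product. In the first row of the table, with glucose in mg/dL (an assumption, since no unit is stated; the direction is the same in mmol/l), QUICKI goes from 1 / (log₁₀ 15 + log₁₀ 110) = 0.311 to 1 / (log₁₀ 15 + log₁₀ 95) = 0.317. That is a 2.0% rise, meaning more sensitive, while the written HOMA-IR reports 15.8% more resistance in the same patient.

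**The case against.** The strongest reply is that little in the plan depends on this line. HOMA-IR is not among the numbered dependent variables, where insulin sensitivity is defined by Matsuda. HOMA-IR is named as a trial measurement only at baseline and in the methods list. The mid-term section speaks of indices in general and the final-visit section names none, so a comparison of HOMA-IR over time or between arms is inferred. No eligibility rule or planned analysis applies the cut-offs. The slash may be a slip in typing, translation or file conversion for a multiplication sign. The background gives the right form, and an analyst who saw values near 0.1 would probably notice.

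Most of this stands, and it limits the consequence: the main insulin sensitivity result is safe, and the cut-offs serve only to show that the scale is wrong. It does not remove the error. The methods list says these calculations will be used, and the fasting values they need are collected at baseline, 6 months and 12 months. A conversion fault is possible but not shown; multiplication signs are intact in the Matsuda and HOMA-B lines of the same list. Whatever its origin, the operative formula as it stands specifies a division.

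**Conclusion.** The concern holds. The methods formula for HOMA-IR contradicts the background formula, reverses the contribution of glucose, and gives values 31 to 48 times smaller than the product form at entry glucose levels. Followed literally, it can report improvement as worsening whenever glucose falls by a larger percentage than insulin.

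The contradiction and the reversal follow from the two formulas alone. The percentages in the examples rest on assumed insulin values and assumed changes, so they show the mechanism and are not an estimate of bias. Any distortion of the difference between arms depends on insulin changes that the documents do not give. This should be corrected before HOMA-IR is analysed, but it does not threaten the design.

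**What to change.** In Laboratory procedures and techniques, replace the division by a multiplication: HOMA-IR = (fasting insulin in mU/l × fasting glucose in mmol/l) / 22.5, as in the background. Confirm that the calculation sheet or analysis code uses this form at every visit where HOMA-IR is derived, and recalculate any values already obtained with the ratio. The cost is one symbol in the text. Fasting insulin and glucose are already collected, so no new data, visits or change in sample size are needed.

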## **STATISTIC ANALYSIS**

The data will be presented with descriptive statistics, mean and standard or median deviation and interquartile range, as well as percentages and incidence. For comparisons of numerical variables between the study groups, we will use Student's t if the distribution of the data follows a normal pattern, otherwise the Mann-whitney U test will be used; To compare qualitative variables we will use Chi square. Delta analysis will be performed for differences between groups. It will be considered significant when the value of p is  $<0.05$ . For the analysis and presentation of the data we will use the SPSS Version 15 and GraphPad Prism 5 programs.

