### **MATERIAL AND METHODS**

**Type of study:** Single Center Parallel Clinical trial, randomized, double blind

**Study universe:** Mexican patients with mixed prediabetes and obesity.

**Study population:** Mexican patients with mixed prediabetes and obesity, from the State of Guanajuato.

**Location:** Regional High Specialty Hospital of Bajío and Division of Health Sciences of the University of Guanajuato, León, Gto.

**Type of sampling:** Non-probabilistic, of consecutive cases.

**Sample size:** The sample size calculation was performed based on the formula to compare proportions. We expect that quadruple therapy (linagliptin + empagliflozin + metformin + lifestyle modifications), improve at least 75% the outcome variables (insulin resistance, pancreatic islet function and cardiovascular function), at 6 months of initiated the intervention, as long as the standard therapy (metformin + lifestyle modifications) achieves only 30% [69-71, 73], so that the study is designed to detect a minimum difference of 45% between the study groups with a type I (alpha) error of 0.05 and a sample power of 80%, and according to the following formula [108]:

$$n = \frac{(Z_{\alpha/2} + Z_{\beta})^2 p_1(1-p_1)(r + 1)}{(d)^2 r}$$

Where,

$$(Z_{\alpha / 2} + Z_{\beta})^2 = 7.9$$

p1 = proportion of individuals in the best treatment who did not achieve improvement = 0.25

p2 = proportion of individuals in the worst treatment who did not achieve improvement = 0.70

r = ratio of individuals in the treatment groups = 1

d = difference expected to be found = 0.45

n = 14 + 20% of losses = 17 patients per group

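### With no missing-data method, the 12-month tests of continuous outcomes cannot use the month-6 results of patients who leave afterwards, and this can bias the comparison in either direction

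*Combined protocol and SAP*

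**What the plan says.** All references are to the combined protocol and SAP.

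- **Statistic analysis.** Numerical variables are covered by one rule: "For comparisons of numerical variables between the study groups, we will use Student's t if the distribution of the data follows a normal pattern", with Mann-Whitney otherwise, and an unspecified delta analysis. No time point, analysis population, imputation or repeated-measures model is given.
- **Sample size (Material and Methods).** Losses appear only as an inflation: "n = 14 + 20% of losses = 17 patients per group". When they occur is not stated. The expected improvement in that paragraph is set at 6 months.
- **Timing of the outcome.** Specific goals 2 and 3, the operational definition of the intervention, and dependent variable 1 all use 12 months. Specific goal 5 compares the groups at the end of the intervention.
- **Mid-term evaluation (month 6).** Both arms repeat the OGTT: "During this test blood samples will be taken at 0, 30, 60, 90 and 120 minutes to determine glucose and insulin". Cardiovascular and renal function are also re-evaluated.
- **Completion of the study (month 12).** OGTT, echocardiography and renal function are measured again.

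**The concern.** A two-sample test of 12-month values, or of change to 12 months, needs a 12-month value. Someone who leaves at month 8 has a month-6 Matsuda index, beta-cell indices and echocardiogram, and none of these can enter. The 20% inflation protects the number of evaluable patients but does nothing about which patients remain.

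Patients are seen monthly with a fasting glucose and have a full OGTT at month 6, so leaving related to response is plausible, though the documents cannot show it. If it happens, those who stay look better than the arm they represent. Insulin resistance, islet function and cardiovascular function are the trial's stated goal, so this affects its main continuous comparisons. The information that could correct it is already scheduled.

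**Working it through.** **The plan's own figure.** Inputs from the Sample size paragraph: squared Z sum 7.9, p1 = 0.25, r = 1, d = 0.45.

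n = 7.9 × 0.25 × 0.75 × 2 / 0.45² = 2.9625 / 0.2025 = 14.63, stated as 14. Then 14 × 1.20 = 16.8, stated as 17. The plan therefore expects 17 − 14 = 3 losses per arm, 6 of 34 (18%).

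**Assumptions, because the documents give no SD, correlation or dropout pattern.** Outcomes are in SD units, higher is better, and the month-6 to month-12 correlation ρ is 0.5 to 0.8. All leaving occurs after month 6 and depends on the month-6 value.

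**Check 1: sharp rule, true effect 0.8 SD at both visits.** Everyone below a control-arm percentile at month 6 leaves, in either arm. The mean of those who stay exceeds the arm mean by ρλ, with λ = φ(c)/(1 − Φ(c)) and c the cut-off relative to that arm's mean. The bias in the difference is −ρ(λ_control − λ_quadruple).

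- 20% of controls leave: λ_control = 0.280/0.80 = 0.350 (c = −0.842) and λ_quadruple = 0.104/0.950 = 0.109 (c = −1.642). The gap is 0.241. For ρ = 0.5, 0.7, 0.8 the bias is −0.12, −0.17, −0.19, so the completers' estimate is 0.68, 0.63, 0.61. About 5% of the quadruple arm also leaves, giving a total loss of 12.5%.
- 10% of controls leave: λ_control = 0.195 and λ_quadruple = 0.047. The gap is 0.148. The bias is −0.07, −0.10, −0.12, so the estimate is 0.73, 0.70, 0.68.

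Simulation with 17 per arm gives the same completers' estimates to within 0.01. Using the month-6 values gives 0.80 to 0.81 throughout. The SD of the estimates is 0.33 to 0.36 for completers and 0.35 to 0.37 with month-6 data.

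**Check 2: graded rule.** The probability of leaving rises as the month-6 value worsens (log-odds slope 1 to 2 per SD), with 20% lost overall, ρ = 0.5 to 0.7 and 400,000 simulated patients per arm.

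| Who leaves | True effect (SD) | Completers' bias in the difference (SD) |
|---|---|---|
| Same rule in both arms | 0 | 0 (within 0.004) |
| Same rule in both arms | 0.5 | −0.03 to −0.08 |
| Same rule in both arms | 1 | −0.06 to −0.16 |
| Poor responders from control; quadruple loses 20% at random | 0 to 1 | −0.09 to −0.18 |
| Poor responders from quadruple; control loses 20% at random | 0 to 1 | +0.09 to +0.19 |

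Negative values understate quadruple therapy. Under the same-rule scenarios single-arm means are too favourable by 0.06 to 0.26 SD. Predicting month 12 from month 6 within each arm and averaging over all randomized patients leaves at most 0.005 SD of bias in the difference in every row.

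**Scale.** The largest bias, 0.19 SD, is a little over half a standard error (0.19/0.33 = 0.58). With 14 per arm, the difference detectable at 80% power is √7.849 × √(2/14) = 1.06 SD.

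**The case against.** The strongest case is that the plan nowhere says leavers are discarded. That is inferred from silence, and the recall at 12 months does not exclude patients who stopped treatment, so stopping need not mean a missing value. This stands as a limit on the wording. It does not remove the gap, because no stated method can use a patient whose 12-month value is missing.

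The Sample size paragraph places its expected improvement at 6 months and does not place the losses after month 6. This also stands. If most losses come earlier, there are fewer month-6 results to recover and the gain is smaller.

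Three stronger readings are tempting but unsupported:

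- *The treatment effect will be underestimated.* The direction depends on which arm loses poor responders. The trial is described as double blind, and nothing says patients are told their results, so no direction can be assumed.
- *The completers' test is invalid whenever leaving depends on response.* With no true effect and the same leaving mechanism in both arms there is no bias. Simulated t-test rejection under the sharp rule was 4.7% to 5.3%.
- *All continuous outcomes can be rescued.* HbA1c is measured only at the start and end. Inflammation markers and DEXA are not listed at month 6.

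Finally, overall accuracy changes little. Under the sharp rule, root mean squared error is 0.347 to 0.355 SD for completers against 0.349 to 0.352 with month-6 data when 10% of controls leave, and 0.373 to 0.379 against 0.356 to 0.369 when 20% leave. That is a tie in the first case and a gain of at most about 7% in the second. The argument for changing the plan is removal of a possible bias at almost no cost. It is not a large gain in precision.

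**Conclusion.** The point holds in a conditional form. As written, a patient without a 12-month value drops out of the 12-month comparison even when month-6 results are in hand. If leaving depends on the month-6 response, the arm means are biased, and so is the difference when there is a true effect or leaving differs by arm.

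The size is about 0 to 0.19 SD in either direction, against a standard error of about 0.33 to 0.36 SD. These figures rest on an assumed correlation and leaving rule, and on placing all losses after month 6. The sharp cut-off is a severe version. The plan should be changed, but the documents do not show that bias will occur.

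**What to change.** In Statistic analysis, state that the continuous measures taken at both month 6 and month 12 (OGTT insulin-sensitivity and beta-cell indices, echocardiography, renal function) will be analysed with a repeated-measures mixed model. Its terms are arm, visit, arm-by-visit and baseline value, with unstructured covariance over the two visits. Log-transform skewed indices. Include every randomized patient with a month-6 or month-12 value, take the 12-month difference from the model, and keep the completers' test as a sensitivity analysis. State in the Sample size paragraph when the 20% losses are expected, and reconcile its 6-month reference with the 12-month outcome used elsewhere.

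The cost is wording only, with no new visits, data or patients. The standard error is a few percent larger (about 3% to 9% in the simulations). The model assumes missing at random: leaving may depend on values already observed, but not additionally on the unseen 12-month value. It does not recover patients who leave before month 6. Month-6 data add nothing for HbA1c, inflammation markers or DEXA. The dichotomous outcome (dependent variable 1, regression of hyperglycemia and glucose intolerance) and its chi-square test are unchanged and need their own rule for missing 12-month results.

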### **Specific goals:**

1. Identify patients with glucose intolerance and obesity who may enter the study.
2. To assess the effect at 12 months with treatment with metformin 1700 mg / d and lifestyle modifications on insulin resistance, pancreatic islet function, and cardiovascular function in a group of patients with mixed prediabetes and obesity.
3. To assess the effect at 12 months of treatment with the combination of linagliptin 2.5 mg / metformin 850 mg every 24 h + Empagliflozin 12.5 mg / metformin 850 mg every 24 h and lifestyle changes on insulin resistance, the function of Pancreatic islet and cardiovascular function in a group of patients with mixed prediabetes and obesity.

4. Evaluate and compare cardiovascular risk markers (TNF $\alpha$ , IL6, hsPCR) before and after treatments in the 2 study groups.
5. Compare insulin resistance and pancreatic islet function between the study groups at the end of the intervention.
6. Evaluate and compare glucose metabolism using OGTT at the beginning and end of treatment in the study groups.

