### **Secondary objectives**

- Evaluate the percentage of patients who recovered glucose normotolerance after the intervention in each of the study groups.
- Evaluate and compare the changes in body composition, through body composition analysis by DEXA, in the two study groups at the beginning and at the end of the intervention.
- Evaluate therapeutic adherence in the study groups.

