### **HYPOTHESIS**

Quadruple therapy (linagliptin + empagliflozin + metformin + lifestyle modifications) has a greater effect on pancreatic islet function, insulin resistance and cardiovascular function compared to standard therapy (metformin + lifestyle modifications) in patients with mixed prediabetes and obesity.

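### The analysis section tests every comparison at p<0.05 with no primary measure named among three hypothesis domains, so the stated 5% error rate is not secured; baseline values enter only through an undefined delta

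*Combined protocol and SAP*

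**What the plan says.** The Statistic analysis section is one paragraph. Numerical variables are compared by Student's t if normally distributed, "otherwise the Mann-whitney U test will be used"; qualitative variables are compared by chi-square. It then says "Delta analysis will be performed for differences between groups. It will be considered significant when the value of p is" below 0.05. It does not say whether delta is absolute or percent, which variables it covers or which test it uses.

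The Hypothesis is that quadruple therapy "has a greater effect on pancreatic islet function, insulin resistance and cardiovascular function compared to standard therapy". The three domains are joined by 'and' and are not ranked. The measures given for them are:

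- **Insulin resistance** (Laboratory procedures and techniques): HOMA-IR, Matsuda, QUICKI.
- **Islet function** (Dependent variables 3 and 4; Laboratory procedures): a 0-30 minute insulin-to-glucose increment ratio, a ratio of incremental areas over 120 minutes, and HOMA-B. An insulin availability index is also listed and may be the same as variable 3.
- **Cardiovascular function** (Dependent variable 7): ejection fraction, ventricular mass, diastolic and systolic preloads.

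Secondary objectives exist, for example "Evaluate the percentage of patients who recovered glucose normotolerance after the intervention in each of the study groups", but no primary objective is set against them. The Sample size text expects quadruple therapy to "improve at least 75% the outcome variables (insulin resistance, pancreatic islet function and cardiovascular function), at 6 months of initiated the intervention". Specific goal 2 is "To assess the effect at 12 months with treatment with metformin 1700 mg / d and lifestyle modifications on insulin resistance", and the 6-month visit is headed as a mid-term evaluation: "After 6 months of treatment, the patients of both study groups will be summoned". Specific goal 5 is to "Compare insulin resistance and pancreatic islet function between the study groups at the end of the intervention".

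**The concern.** The protocol makes a confirmatory claim: a directional hypothesis, alpha of 0.05 and 80% power. That alpha holds only if the test that decides the claim is fixed in advance. Here the reader cannot tell whether one domain or all three must succeed, nor which index speaks for a domain. A positive result on any of several indices could be reported as support for the hypothesis at a nominal 5%. The undefined delta adds further choice.

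A lesser matter is precision. Baseline values are collected, but they are used only through the delta, and a comparison of end values (goal 5) ignores them. With about 14 evaluable patients per arm, lost precision is expensive.

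**Working it through.** **The plan's own figure.** 7.9 x 0.25 x 0.75 x (1+1) / 0.45² = 14.63, given as 14; 14 x 1.2 = 16.8, given as 17. The figure reproduces apart from truncation. It is powered for one dichotomous proportion, not for any continuous index.

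**Number of indices.** 3 + 3 + 4 = 10, or nine if the two preloads are one item. HOMA-IR in the product form of the background section on prediabetes is proportional to insulin x glucose, and QUICKI is 1/(log insulin + log glucose). They are therefore monotone transforms of each other, and a Mann-Whitney test on end values gives the same p-value for both. The effective count is lower than the nominal one.

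**If any one domain suffices.** The documents give no correlations, so those below are assumptions. Each test is two-sided at 0.05; correlated cases come from simulation with 1,000,000 draws.

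- One test per domain: 1 - 0.95³ = 14.3% if independent; 12.6% at correlation 0.5; 9.8% at 0.8.
- Several indices per domain, correlation 0.8 within domains and 0 to 0.5 between:

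| Indices counted (insulin resistance + islet + cardiac) | Chance of at least one false positive |
|---|---|
| 3+3+4, all listed | 28.0% to 23.8% |
| 2+3+4, HOMA-IR and QUICKI as one | 26.4% to 22.5% |
| 2+3+3, preloads also merged | 25.0% to 21.5% |
| 2+3+1, ejection fraction alone for the heart | 21.0% to 18.1% |

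A within-domain correlation of 0.5 would put the 3+3+4 row at 35.5% to 28.7%.

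**If all three must succeed.** One pre-named test per domain keeps the error at or below 5%. Suppose instead that one domain has no effect and its best index may be chosen afterwards. At within-domain correlation 0.8 to 0.5, the chance that this domain shows significance is 9.8-12.6% for the best of three and 11.5-15.6% for the best of four. This is the error of the joint claim only if the other two domains are certain to succeed. If each has 80% power, independently and with one named test, multiply by 0.8 x 0.8 = 0.64: 0.64 x 9.8% = 6.3% up to 0.64 x 15.6% = 10.0%.

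If each domain had 80% power, joint power would be 0.8³ = 51% at correlation 0, 61% at 0.5 and 66% at 0.7. This is illustrative, since no domain measure has been powered.

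**Baseline adjustment.** Take the end-value variance as 1 and let r be the baseline-to-12-month correlation (not given in the documents). Delta has variance 2(1 - r). ANCOVA at n = 14 per arm has (1 - r²)(1 + 1/(2n - 4)) = (1 - r²) x 1.042.

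| r | Better of end value and delta | ANCOVA | Ratio | Power where the better one has 80% |
|---|---|---|---|---|
| 0.3 | 1.00 | 0.948 | 0.948 | 82% |
| 0.5 | 1.00 | 0.781 | 0.781 | 89% |
| 0.7 | 0.60 | 0.531 | 0.885 | 84% |

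Break-even: 1 - r² = 24/25 gives r = 0.20, and 1 + r = 48/25 gives r = 0.92. Outside that interval there is no gain.

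Scale matters. In an illustrative lognormal simulation (log SD 1, log shift 1, 14 per arm, r = 0.3/0.5/0.7), the better Mann-Whitney analysis had 69/70/88% power, log-scale ANCOVA 75/82/94% and untransformed ANCOVA only 53/58/72%.

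**The case against.** The strongest reply is that both the Hypothesis and the Sample size text join the domains with 'and', so the natural reading is that all three must succeed. That reading removes the inflation if one test per domain is named. It stands as far as it goes, and it makes the any-one-domain figures the less natural case. But no index is named, so choice within a domain remains, and joint power then becomes the problem.

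Second, the index count can be overstated. This stands too: HOMA-IR and QUICKI nearly coincide, the preloads may be one item, and the only indicator given for cardiovascular function is a percentage, which fits ejection fraction best. The lower end of the range allows for this.

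Third, comparing changes is valid in a randomised trial. It is; the loss is one of precision only.

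A reader might draw four stronger conclusions that the documents do not support:

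- **A 40% error rate** (1 - 0.95¹⁰) needs ten independent tests, but many of the indices are built from the same glucose and insulin values.
- **Two to three times 5% under the all-three reading** is not a general result; it needs the other two domains to be certain to succeed.
- **Two competing primary time points** are not set. The goals, Dependent variable 1 and the final measurements all use 12 months; only the Sample size text uses 6.
- **A biased treatment effect from leaving out baseline** does not follow under randomisation.

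**Conclusion.** The point holds. Followed as written, the plan does not deliver its stated 5% error rate, because no primary measure, decision rule across domains or multiplicity rule exists anywhere in the document.

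The size depends on a reading that the documents leave open. It is about 10-14% (one test per domain) or roughly 18-28% (listed indices) if any domain suffices. If all must succeed there is no inflation with pre-named tests, and at most about 10-16% with free choice in one null domain. These figures rest on assumed correlations, since the documents give none; lower within-domain correlation would raise those for several indices. The absence of a primary measure rests on the text alone. The baseline point is secondary, a modest gain in precision for r between about 0.2 and 0.92. The matter should be settled before any unblinded comparison.

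**What to change.** In Statistic analysis:

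1. **Name one primary measure at 12 months**, two-sided 0.05. There are two candidates. The dichotomous glucose outcome of Dependent variable 1 fits the proportion-based sample size, but it must be reconciled with the secondary label on recovery of normotolerance and is not itself one of the three hypothesis domains. The Matsuda index is defined alike in both places where it appears, but it needs a new sample-size basis with an assumed SD and, if adjusted for baseline, a correlation.
2. **Align the 6 months in the Sample size text** with the chosen time point.
3. **If the primary succeeds, test one pre-named measure for each remaining domain** in fixed order or by Holm. Label all other indices and the 6-month results secondary or exploratory.
4. **Define delta** as absolute or percent wherever it is reported.
5. **For continuous measures, replace the unadjusted comparison by ANCOVA** with the measure's own baseline as covariate, on the log scale for strictly positive skewed measures. For the ratios in Dependent variables 3 and 4, which can be zero or negative, pre-specify a rank-based ANCOVA.
6. **Reconcile the HOMA-IR formulas** before it is analysed: the background section shows a product, and Laboratory procedures appears to show a quotient (possibly a text-extraction fault).

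No new measurement is needed. The costs are that fewer results can be called significant, the other domains go untested if the primary fails, each model uses one degree of freedom (about 4% on the variance at 14 per arm), the rank-based test gives no adjusted difference on the measured scale, and the sample-size text must be restated.
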